#### **Study Design**

We conducted a randomized, double-blind, placebo-controlled trial in a single cardiothoracic surgery program at two hospitals in a large academic health system. Prior to beginning the trial, we obtained institutional review board approval from Duke University Medical Center, FDA approval for an investigational new drug application, and registered the trial at ClinicalTrials.gov (NCT02498769).

#### **Participants**

The trial enrolled adult patients undergoing CABG, valve surgery, or CABG/valve surgery performed via sternotomy using cardiopulmonary bypass. Patients  $>90$  or  $<50$  years of age, those with long-standing persistent AF, prior cardiac surgery, left ventricular ejection fraction  $<25\%$ , preoperative inotropic support, hepatic dysfunction (AST or ALT  $> 1.5 \times$  upper limit of normal), renal dysfunction (serum creatinine  $> 2.0$  mg/dL), known sensitivity to botulinum toxin, debilitating neuromuscular disease, or those with a history of second-degree or third-degree atrioventricular block were excluded from the study. All patients gave both verbal and written consent to participate in the trial.

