#### **Procedures**

The attending cardiac surgeon performed injections immediately after initiation of cardiopulmonary bypass, prior to the primary surgical procedure. Study solution (1mL consisting of 50 units onabotulinumtoxinA or 1mL placebo) was injected using a 27g needle under direct vision into all five epicardial fat pads, including the anterior fat pad, and the fat pads associated with each pulmonary vein. The remainder of perioperative care was managed according to the primary team.

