#### **Outcomes**

The primary end point of this study was time to  $>30$  seconds of in-hospital POAF as assessed by continuous telemetry during the postoperative hospitalization. Pre-specified secondary end points included the incidence of POAF, and among those developing POAF the duration of first POAF episode, in-hospital burden of POAF (percent of postoperative hospitalization spent in AF), proportion of recurrent (greater than one episode lasting  $>30$ s) or prolonged (two days or greater in duration) POAF, and need for POAF treatment (medications administered for rate control, rhythm control, or electrical cardioversions for POAF). Additionally, the ICU and hospital LOS were compared between groups. As an exploratory analysis, we also examined the incidence of

hemodynamically significant new-onset POAF, resulting in rapid ventricular response (heart rate > 100 BPM) and hypotension (systolic blood pressure < 100 mmHg).

Safety end points included the incidence of any adverse event or postoperative complication, the incidence of adverse events prolonging LOS, and postoperative mortality. Additionally, duration of postoperative mechanical ventilation and the incidence of reintubation were compared between groups.

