### ***Statistical Analysis***

Based on a pilot trial showing a pronounced reduction (30 day relative risk reduction 78%) in POAF after injecting BoNTA into the epicardial fat pads, we anticipated a significant reduction in the risk for POAF with epicardial BoNTA injection in our cohort. Our study sought to include valve surgery patients, which would result in a higher-risk population for POAF. Based upon a two-tailed alpha of 0.05, an estimated POAF incidence of 40% in the control group, and a total sample size of 130 (n=65 in each arm), we prospectively determined 80% power to detect a 40% difference in relative risk (corresponding to a hazard ratio of 0.4) between treatment groups for the primary outcome.

Analyses were based on the intention-to-treat principle in all patients who received epicardial injection (modified intention-to-treat analysis). Patient characteristics were summarized by standard descriptive statistics and were compared between groups using t-tests, Wilcoxon rank sum tests, Chi-square tests, or Fisher exact tests as appropriate. The Kaplan-Meier method was used to construct non-parametric estimates of the distribution of time to first POAF event. Adjustment of treatment effect for baseline factors previously found associated with POAF outcome was accomplished using Cox proportional hazards modeling. The proportional hazards assumption was confirmed via log-log plots, plots of Schoenfeld residuals by time, and testing of a group-time interaction in the model. Secondary analyses were conducted via parametric and non-parametric assessments as appropriate.

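### Does silence about rhythm at surgery let atrial fibrillation carried into telemetry dilute the primary hazard ratio?

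*Combined protocol and SAP*

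**What the plan says.** The only AF-related exclusion, under Participants, is in the phrase "those with long-standing persistent AF, prior cardiac surgery". Paroxysmal AF, shorter persistent AF and AF on the day of surgery are not mentioned.

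Under Outcomes, the primary event is an episode of more than 30 "seconds of in-hospital POAF as assessed by continuous telemetry during the postoperative hospitalization". Neither a time origin nor a period of sinus rhythm beforehand is specified. Two phrases point to onset: the secondary endpoints are described "among those developing POAF the duration of first POAF episode", and the Kaplan-Meier curves are "non-parametric estimates of the distribution of time to first POAF event". The qualifier new-onset appears only with the exploratory haemodynamic outcome.

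The Procedures section says the surgeon "performed injections immediately after initiation of cardiopulmonary bypass, prior to the primary surgical procedure", so treatment comes before any postoperative monitoring. The Statistical Analysis section analyses outcomes "in all patients who received epicardial injection (modified intention-to-treat analysis". On covariates it says: "Adjustment of treatment effect for baseline factors previously found associated with POAF outcome was accomplished using Cox proportional hazards modeling". The factors are not listed. The planning claim is "80% power to detect a 40% difference in relative risk (corresponding to a hazard ratio of 0.4", with 65 patients per arm and 40% control incidence.

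**The concern.** A patient in AF at surgery who is still in AF when telemetry starts meets the 30-second criterion at once. If that happens equally often in both arms, these events carry no information about prevention but still enter the Cox model and the Kaplan-Meier curves. A true hazard ratio of 0.40 would then be estimated closer to 1. The design expects only about 38 events, so a handful of such patients could matter: 5% of 130 is 6 or 7 people. Neither the subgroup list nor the unlisted adjustment factors show that rhythm is handled elsewhere. At stake would be power for the primary comparison and the size of the reported effect.

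**Working it through.** **1. The plan's own figure.** Inputs from Statistical Analysis: 65 per arm, 40% control incidence, HR 0.4, two-sided alpha 0.05.

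- Treated incidence: 1 − 0.60^0.4 = 18.5%.
- Expected events: 65 × (0.400 + 0.185) = 38.0.
- Schoenfeld power: Φ(√38.0/2 × |ln 0.4| − 1.96) = Φ(0.86) = 80.6%.

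The stated 80% reproduces from HR 0.4. A 40% relative reduction (40% to 24%) would instead imply ln 0.76/ln 0.60 = 0.54; that is a separate matter. Simulated log-rank power under the same inputs is 78%, the reference below.

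**2. Hand approximation of the pull.** Let a fraction g of each arm have an event at time zero regardless of treatment, with the rest keeping HR 0.40 and 40% control incidence. Weight the log hazard ratio by events: (1 − g) × 38.0 events at ln 0.4 = −0.916, and 130 × g events at 0.

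- g = 0.02: 37.3 + 2.6 = 39.9 events; −0.916 × 37.3/39.9 = −0.857; HR 0.42.
- g = 0.05: 36.1 + 6.5 = 42.6 events; −0.777; HR 0.46.
- g = 0.10: 34.2 + 13.0 = 47.2 events; −0.664; HR 0.51.

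Large-sample simulation gives 0.46 at 5% and 0.52 at 10%, so the mechanism is confirmed. Only g matters here: a 10% share in AF with half persisting acts like a 5% share with all persisting.

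**3. Power across assumed shares and persistence.** Simulation of 65 per arm, 20,000 trials per cell, exponential times. Every share and persistence rate is an assumption. Cells show unstratified / rhythm-stratified log-rank power (%).

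| Persistence, control / treated | 2% in AF | 5% | 10% | 15% |
|---|---|---|---|---|
| 100% / 100% | 74 / 78 | 69 / 77 | 60 / 74 | 53 / 71 |
| 50% / 50% | 77 / 78 | 74 / 75 | 69 / 72 | 65 / 69 |
| 75% / 60% | 76 / 78 | 75 / 78 | 71 / 77 | 69 / 76 |
| 50% / 35% | 78 / 78 | 78 / 78 | 76 / 78 | 75 / 78 |
| 50% / 25% | 79 / 79 | 79 / 79 | 80 / 81 | 81 / 82 |

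The pull vanishes once treated persistence is about 0.4 times control persistence. At a 10% share with all controls persisting, the large-sample HR is 0.52, 0.48, 0.44, 0.42 and 0.40 at ratios 1, 0.8, 0.6, 0.5 and 0.4.

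**4. Type I error.** With no treatment effect and equal persistence, the stratified test rejects 4.7% to 5.2% of the time. The unstratified test is also safe, because under the null the time-zero events are balanced by randomisation.

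**5. What a rhythm-stratified model would buy.** With half persisting in both arms it recovers about 1, 2, 3 and 4 points at the four shares. At a 10% share the HR moves only from 0.47 to 0.46. When all persist, the result depends on tie handling: the stratified HR is 0.40 with exact ties but 0.52 with Breslow ties. A small check (about 225 to 245 trials per cell, Monte Carlo error about 3 points) at a 10% share compared rhythm as an ordinary Cox covariate with rhythm as a stratum. Power was 66.7% and 66.7% when all persist, and 71.7% and 71.2% when half do.

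**The case for a change.** The strongest case for acting is that a primary endpoint should not leave two analysts free to count the same patient differently. Attaching new-onset to an exploratory outcome alone suggests it was not meant for the primary one. The adverse cells are not trivial: 60% power at a 10% share with full persistence, and 50% if the planned 40% control incidence is taken to include the carried-over cases. A clarifying sentence costs almost nothing.

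The ambiguity stands: the text supports both readings. What does not follow is a defect in the analysis. The large losses need several things at once: many patients in AF at surgery, nearly all still in AF at telemetry, those cases counted as postoperative AF, and no treatment effect on persistence. The documents establish none of these, and the last is doubtful because duration and burden of AF are themselves treated as outcomes the injection might change.

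The power figures are also for a log-rank test, whereas the plan names an adjusted Cox model. If rhythm is among its unlisted factors, stratification adds almost nothing. Finally, if carried-over AF belongs to the endpoint, the hazard ratio in the mixed population is the correct effect on that endpoint. It is diluted only relative to a different target, patients not in AF.

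**Conclusion.** The concern identifies missing detail rather than a wrong choice. The time origin and the status of AF present at the start of telemetry have to be settled when the endpoint is derived, and analysts will settle them then. On the onset reading, which the plan's wording about developing AF and a first event supports, the dilution does not arise. On the literal reading the test remains valid. The cost is then 1 to 4 points of power at an assumed 2% share (half or all persisting), nothing if the injection roughly halves persistence, and a serious loss only at assumed shares of about 10% or more with near-complete persistence in both arms.

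A stratified primary model would depend on one of the two readings and on the tie method, would need a baseline variable the documents do not say was collected, and may repeat adjustment already planned. That is too little expected gain to ask for a change. The conclusion rests on assumed shares and persistence rates. A high documented proportion in AF at surgery, with those cases counted as events, would alter it.

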#### **Randomization and Masking**

Eligible patients were randomly assigned utilizing a computer-generated mixed block size in a 1:1 ratio to receive epicardial injections of either 250 units (5 mL) of onabotulinumtoxinA (BotoxTM) or an equivalent volume of identical normal saline (placebo injection) equally amongst five identical syringes.

#### **Procedures**

The attending cardiac surgeon performed injections immediately after initiation of cardiopulmonary bypass, prior to the primary surgical procedure. Study solution (1mL consisting of 50 units onabotulinumtoxinA or 1mL placebo) was injected using a 27g needle under direct vision into all five epicardial fat pads, including the anterior fat pad, and the fat pads associated with each pulmonary vein. The remainder of perioperative care was managed according to the primary team.

#### **Outcomes**

The primary end point of this study was time to  $>30$  seconds of in-hospital POAF as assessed by continuous telemetry during the postoperative hospitalization. Pre-specified secondary end points included the incidence of POAF, and among those developing POAF the duration of first POAF episode, in-hospital burden of POAF (percent of postoperative hospitalization spent in AF), proportion of recurrent (greater than one episode lasting  $>30$ s) or prolonged (two days or greater in duration) POAF, and need for POAF treatment (medications administered for rate control, rhythm control, or electrical cardioversions for POAF). Additionally, the ICU and hospital LOS were compared between groups. As an exploratory analysis, we also examined the incidence of

hemodynamically significant new-onset POAF, resulting in rapid ventricular response (heart rate > 100 BPM) and hypotension (systolic blood pressure < 100 mmHg).

Safety end points included the incidence of any adverse event or postoperative complication, the incidence of adverse events prolonging LOS, and postoperative mortality. Additionally, duration of postoperative mechanical ventilation and the incidence of reintubation were compared between groups.

### ***Statistical Analysis***

Based on a pilot trial showing a pronounced reduction (30 day relative risk reduction 78%) in POAF after injecting BoNTA into the epicardial fat pads, we anticipated a significant reduction in the risk for POAF with epicardial BoNTA injection in our cohort. Our study sought to include valve surgery patients, which would result in a higher-risk population for POAF. Based upon a two-tailed alpha of 0.05, an estimated POAF incidence of 40% in the control group, and a total sample size of 130 (n=65 in each arm), we prospectively determined 80% power to detect a 40% difference in relative risk (corresponding to a hazard ratio of 0.4) between treatment groups for the primary outcome.

Analyses were based on the intention-to-treat principle in all patients who received epicardial injection (modified intention-to-treat analysis). Patient characteristics were summarized by standard descriptive statistics and were compared between groups using t-tests, Wilcoxon rank sum tests, Chi-square tests, or Fisher exact tests as appropriate. The Kaplan-Meier method was used to construct non-parametric estimates of the distribution of time to first POAF event. Adjustment of treatment effect for baseline factors previously found associated with POAF outcome was accomplished using Cox proportional hazards modeling. The proportional hazards assumption was confirmed via log-log plots, plots of Schoenfeld residuals by time, and testing of a group-time interaction in the model. Secondary analyses were conducted via parametric and non-parametric assessments as appropriate.

Secondary analysis of incidence of POAF was conducted via univariable and adjusted logistic regression with the same baseline characteristics as in the primary outcome model. Heterogeneity of treatment effect was explored in patient subgroups defined by surgery type, POAF risk as assessed by the Multicenter Study of Perioperative Ischemia (McSPI) AFRisk index, preoperative angiotensin converting enzyme inhibitor (ACEi) use, beta-blocker use, diabetes, and congestive heart failure. We studied differences in ICU and hospital LOS via Wilcoxon rank sum tests. In order to characterize severity of POAF between groups, we explored group differences among patients who developed POAF in duration of first POAF, initial ventricular rate, total POAF duration (cumulative duration of all in-hospital POAF), and total POAF burden (percent of postoperative hospital LOS spent in AF) via Wilcoxon rank sum tests. We compared the incidence of recurrent POAF, hemodynamically significant POAF, two or greater days of POAF, and need for treatment for AF via Chi-Square or Fisher exact tests. We investigated differences in the incidence of safety endpoints via Chi-Square or Fisher exact tests, and used a Wilcoxon rank sum test to explore differences in duration of postoperative mechanical ventilation.

Because multiple comparisons of secondary outcomes were performed without post-hoc adjustment of the significance level, these outcomes should be interpreted as

exploratory. All comparisons were 2-tailed and significance was set at  $p<0.05$ . Analyses were performed using SAS version 9.4 (SAS Inc., Cary, NC). A data safety monitoring board consisting of a cardiothoracic surgeon, cardiothoracic anesthesiologist, cardiac electrophysiologist, and biostatistician examined blinded, aggregate adverse event data at 10%, 25%, and 50% accrual in order to ensure adequate safety of the study.

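### A 40% relative risk reduction is not a hazard ratio of 0.4: with 65 per arm, power for the stated 40% reduction is about 50%, and the 80% belongs to a 54% reduction

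*Combined protocol and SAP*

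**What the plan says.** The primary endpoint, defined in Outcomes, is time to the first in-hospital POAF lasting more than 30 seconds. The only sample-size justification is in Statistical Analysis. Its inputs are "Based upon a two-tailed alpha of 0.05", "an estimated POAF incidence of 40% in the control group", and 130 patients split equally. From these it concludes: "we prospectively determined 80% power to detect a 40% difference in relative risk (corresponding to a hazard ratio of 0.4) between treatment groups".

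The section gives no formula, expected event count, treated-arm incidence or allowance for loss. It cites a pilot trial with a 78% relative risk reduction at 30 days as the reason to expect a large effect, and it analyses time to POAF with Kaplan-Meier estimates and a Cox model whose proportional hazards assumption is checked.

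**The concern.** The sentence states the target effect twice, as a relative risk and as a hazard ratio, and says the two correspond. Once the control incidence is fixed and hazards are proportional, each determines the other, so the claim can be checked directly. It matters because this is the plan's only statement of what the primary comparison can detect. A reader who takes the 40% relative reduction at face value will put the type II error at 20% for a fall from 40% to 24%. If the error is much larger, a non-significant result could be taken as fair evidence against a 40% reduction when the trial had little ability to find one.

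**Working it through.** **Inputs**, all from Statistical Analysis: control incidence p0 = 0.40; 65 patients per arm; two-sided alpha 0.05 (z = 1.96). Equal allocation is confirmed in Randomization and Masking.

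**Formulas.** Under proportional hazards, with incidence read as cumulative over the hospital stay:

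- HR = ln(1 − p1) / ln(1 − p0), or equivalently p1 = 1 − (1 − p0)^HR
- expected events d = 65 × (p0 + p1)
- power (Schoenfeld) = Φ(|ln HR| × √(d/4) − 1.96)

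**Step 1: reproduce the plan's 80%.** Take HR = 0.4.

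- p1 = 1 − 0.60^0.4 = 0.185
- relative risk = 0.185/0.40 = 0.46, a 54% relative reduction
- d = 65 × 0.585 = 38.0
- power = Φ(0.916 × √9.50 − 1.96) = Φ(0.865) = 80.6%

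Working backwards, 80% power for HR 0.4 needs 38 events, and 38 / 0.2924 = 130 patients, where 0.2924 is the average incidence over the two arms. This matches the plan's total, so the sample size was evidently derived from the hazard ratio.

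**Step 2: the 40% relative reduction.**

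- p1 = 0.60 × 0.40 = 0.24
- HR = ln(0.76)/ln(0.60) = 0.2744/0.5108 = 0.537
- d = 65 × 0.64 = 41.6
- power = Φ(0.621 × √10.4 − 1.96) = Φ(0.044) = 51.7%

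**Step 3: other methods and other readings** (65 per arm, two-sided). Freedman's power is Φ(√d × (1 − HR)/(1 + HR) − 1.96); the two-proportion test uses the pooled variance.

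| Reading | Treated incidence | HR | Events | Schoenfeld | Freedman | Two proportions |
|---|---|---|---|---|---|---|
| HR 0.4 | 18.5% | 0.400 | 38.0 | 80.6% | 75.2% | 77.6% |
| 40% relative reduction | 24% | 0.537 | 41.6 | 51.7% | 49.3% | 49.8% |
| Relative risk 0.4 | 16% | 0.341 | 36.4 | 90.0% | 84.2% | 87.0% |
| HR 0.6 (40% hazard reduction) | 26.4% | 0.600 | 43.2 | 38.9% | 37.5% | 37.6% |
| Odds ratio 0.4 | 21.1% | 0.463 | 39.7 | 68.0% | 63.8% | 65.3% |

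A log-rank simulation (20,000 trials) gave 78.1% for HR 0.4 and 50.4% for the 40% reduction. A one-sided test would raise power for the 40% reduction only to 62% to 64%, and the plan specifies two-sided testing. No row combines a 40% figure for the relative risk, HR 0.4 and 80% power.

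**Step 4: scale.** By Schoenfeld, 80% power for a true 40% reduction needs 82 events, about 82/0.32 = 256 patients. Freedman gives about 272, and the two-proportion test 266 (290 with continuity correction). Alternatively, with 130 patients, the control incidence would have to be near 60% (81.1% by Schoenfeld, 78.9% by two proportions) rather than the 40% assumed.

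**The case against.** The best defence is that the calculation is sound and only a label is wrong. The endpoint is time to event, the plan gives a hazard ratio for it, and that hazard ratio reproduces both 130 patients and 80% power. This stands: the sample size is not miscalculated for HR 0.4.

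A second argument is that the relative-risk phrase is loose and, given the hazard ratio beside it and the 78% pilot reduction, may have meant a relative risk of 0.4. Power would then be 84% to 90%, and the 80% would be conservative. The documents do not settle what was meant, so the shortfall to about 50% is conditional on the literal reading. But the literal reading is the natural one, and the alternative still fails, because a relative risk of 0.4 is HR 0.34. An assumed 10% loss would bring its power to about 80% by Freedman's formula, but loss does not change that hazard ratio, and the plan states no loss allowance.

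Third, the plan contains no rule for interpreting a null result, the document describes a trial already conducted, and the error cannot bias the estimate or inflate type I error. All true. The damage is confined to how the trial's sensitivity is described and hence how a non-significant result may be read. Nothing elsewhere in the document corrects the sentence.

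**Conclusion.** The concern holds. The stated equivalence is wrong at the plan's own control incidence, whatever power formula is used: a 40% relative reduction is HR 0.54, and HR 0.4 is a 54% relative reduction. The 80% attaches to the latter. For the 40% reduction as written, type II error is about 48% to 51%, against the 20% implied.

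The figures assume proportional hazards, 40% as cumulative in-hospital incidence, an unadjusted comparison, and no loss or early censoring. Loss would only lower power for the 40% reduction. The size of the detectable effect depends somewhat on method: exactly 80% power corresponds to a relative reduction of 53.4% (HR 0.403) by Schoenfeld and about 57% (HR 0.37) by Freedman. No standard two-sided method brings it near 40%.

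**What to change.** Replace the power sentence with one that gives a single effect size, its treated-arm incidence and the method. For example: with 65 patients per arm, two-sided alpha 0.05 and 40% control incidence, the trial has about 80% power (Schoenfeld) to detect a hazard ratio of 0.40, that is, POAF falling from 40% to 18.5%, a 54% relative reduction; power for a 40% relative reduction (40% to 24%, hazard ratio 0.54) is about 50%.

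Add that a non-significant primary result will be interpreted from its confidence interval and against this corrected detectable effect.

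The cost is one or two sentences and a less favourable statement of sensitivity. The sample size, endpoint, alpha and analysis are unchanged; the larger totals above show scale and are not a proposal.

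### Does the length-of-stay comparison need a rule for patients who die in hospital?

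*Combined protocol and SAP*

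**What the plan says.** The Outcomes section lists stay alongside the secondary end points: "Additionally, the ICU and hospital LOS were compared between groups". The Statistical Analysis section names the test: "We studied differences in ICU and hospital LOS via Wilcoxon rank sum tests". The analysis set is wide: "Analyses were based on the intention-to-treat principle in all patients who received epicardial injection". Nothing in it removes a patient who later dies.

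Death appears elsewhere, as a safety end point. The Outcomes section includes "the incidence of adverse events prolonging LOS, and postoperative mortality", and the analysis is given by "We investigated differences in the incidence of safety endpoints via Chi-Square or Fisher exact tests". Ventilation time is handled like stay: the plan "used a Wilcoxon rank sum test to explore differences in duration of postoperative mechanical ventilation".

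Neither section says whether a stay ended by death is counted to the day of death, ranked worst, censored or left out. On the standing of these results, the plan says that "multiple comparisons of secondary outcomes were performed without post-hoc adjustment of the significance level" and asks that they be read as exploratory.

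**The concern.** A rank sum test sees only the order of the values. If stay is counted to the day of death, a death on day 2 sits below nearly all ordinary discharges and counts as a good result. An arm with more early deaths would then be partly credited with a shorter hospital stay. In a trial of an injected toxin in cardiac surgery, a false efficiency signal in the arm with more deaths would be an unwelcome error.

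There is also a point about discretion. Counting to death and ranking deaths worst can move the result in opposite directions, and the plan does not say which applies. ICU stay and ventilation time have the same silence.

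**Working it through.** **Inputs.** From the Statistical Analysis section: 65 patients per arm, two-sided tests at 0.05. The documents state no figure for stay, for in-hospital mortality or for the timing of deaths, so there is no figure of the plan's own to reproduce here. The following are assumptions: survivor stay log-normal with median 6 days and log-SD 0.5, the same in both arms; early deaths uniform on days 0.5 to 4; late deaths on days 10 to 20. Simulations used 20,000 trials per setting. Negative z means a shorter stay in the arm with more deaths.

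**Step 1: the most one early death can do.** The null standard deviation of the Mann-Whitney U is √(65 × 65 × 131 / 12) = 214.8. Moving one patient from the middle rank to the lowest changes U by 65/2 = 32.5, so z changes by 32.5/214.8 = 0.151. For the artefact alone to reach 1.96 takes 1.96/0.151 ≈ 13 excess early deaths in one arm, and 13/65 = 20%.

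**Step 2: a fixed imbalance, every death early and all in one arm.**

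| Excess early deaths | Mean z | False finding of shorter stay (nominal 2.5%) |
|---|---|---|
| 1 | −0.13 | 3.1% |
| 2 | −0.27 | 4.4% |
| 3 | −0.41 | 5.7% |
| 4 | −0.55 | 7.3% |

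With three such deaths, an observed z of 1.96 (p = 0.05) corresponds to 1.96 − 0.41 = 1.55 without the artefact, or p = 0.12.

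**Step 3: let the timing vary.** Three excess deaths that are all late give mean z +0.42, the reverse sign. Three excess deaths, each equally likely to be early or late, give mean z +0.01, with 2.5% false shorter and 2.4% false longer.

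**Step 4: let the counts arise from a mortality rate.** Suppose both arms share a mortality of 1%, 2% or 3%. The chance that a given arm has at least three more deaths than the other is then 1.6%, 5.5% or 9.4%. The error rate averaged over such imbalances is what counts:

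| Assumed mortality | Timing | False finding of shorter stay in the higher-mortality arm |
|---|---|---|
| 2% v 2% | all early | 2.5–2.6% (either arm) |
| 4% v 2% | all early | 3.7–3.8% |
| 4% v 2% | half early | 2.5% |

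**Step 5: what the obvious remedy does.** Rank in-hospital deaths worst and keep survivor stays identical. Three excess deaths then give mean z +0.45, a significant longer stay in about 6% of trials and a shorter one in about 0.6%. The shift is about as large as the one in step 2, with the opposite sign.

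**Step 6: ICU stay and ventilation.** With three excess deaths on days 0.5 to 4, ICU stay (assumed medians 1 to 3 days, log-SD 0.6) gives mean z from +0.27 to −0.16. Ventilation (assumed medians 0.25 to 1 day, log-SD 0.7) gives +0.44 to +0.25. ICU stay has no consistent direction. For ventilation the plain test already ranks such deaths as unfavourable.

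**The case for a change.** The strongest case for a change is that the omission is plain, the direction is known for early deaths, and one sentence would close it. A separate mortality comparison does not correct the p-value for stay, and the 0.05 threshold applies to that comparison as to all others. A large, early mortality imbalance would matter: with an assumed 12% against 2%, all early (and log-SD 0.45 for stay), the plain test wrongly favours the higher-mortality arm in 14.4% of trials. Silence also leaves the handling to be chosen after the data are seen.

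Part of this stands. The text does not fix the handling, and a report of stay is easier to read with the number of deaths by arm beside it. The rest is weaker. The inflated rates need deaths that are both unequal and early, and the documents support neither. At 12% against 2%, about 7.8 against 1.3 expected deaths per arm (65 × 0.12 and 65 × 0.02), the mortality comparison would dominate any reading of the trial and nobody would take comfort from a shorter stay. Nor does one sentence settle the matter, because the candidate rules estimate different things. Worst rank gives a composite of death and duration; survivors only describes those discharged alive; time to live discharge treats death as a competing event; and days of bed use properly end at death. The documents give no reason to impose one of these.

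**Conclusion.** No change to the plan is needed. The gap is genuine but small, and analysts can fill it sensibly. Each excess early death is worth at most 0.15 in z, late deaths offset early ones, and equal mortality leaves the error rate at its nominal level. With mortality of 4% against 2%, the false rate of shorter stay is between 2.5% and 3.8%, depending on timing. Stay is an exploratory comparison, deaths are compared in their own right, and neither the primary end point nor the sample size depends on it.

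Prescribing worst ranks would exchange one estimand for another, with a shift of similar size in the opposite direction. Extending such a rule to ICU stay and ventilation has no demonstrated bias in favour of the arm with more deaths behind it, apart from a small shift for ICU stay at the longest assumed median.

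This conclusion rests on assumed stay distributions, death rates and death times, since the documents give none. It would weaken only if one arm had many more deaths than the other and nearly all came before the usual day of discharge. The mortality comparison already in the plan would bring such an imbalance to light.
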